**CBT-I Intervention Protocol Summary.** The CBT-I intervention will be delivered individually and in person by one of the therapists, over six one-hour weekly sessions. In circumstances where in-person visits prevent participation, the CBT-I intervention can be delivered via telephone. The CBT-I protocol is summarized below:

**Session 1: Sleep Education and Introductions to CBT-I and Sleep Diaries.** Participants will receive an overview of CBT-I treatment concepts and approach, in addition to education about sleep regulation processes and the cognitive and behavioral processes involved in the development of insomnia. At the end of the session, they will be instructed in establishing realistic treatment goals and the process for keeping weekly sleep diaries.

**Session 2: Introduction to Sleep Restriction Therapy and Stimulus Control.** The therapist will introduce Stimulus Control and Sleep Restriction Therapy guidelines and rationale. Sleep Restriction Therapy (SRT) is designed to strengthen the homeostatic sleep drive by restricting time in bed to actual sleep time as determined by sleep diary. The sleep “prescription”, or allowable sleep window, is gradually increased over the course of treatment to extend sleep duration. Stimulus Control is a set of instructions designed to strengthen the association between the bed/bedroom and sleep, and to establish a consistent sleep–wake schedule. Participants will receive education and intervention based on treatment targets identified in Session 1 in addition to the sleep pattern information gleaned from the sleep diary review. Sleep hygiene education will be provided for topics that are relevant to the participant (e.g., the effects of alcohol on sleep). An initial “sleep prescription” will be established and participants will be asked to follow this sleep schedule during the upcoming week. Cognitive therapy will be used, as needed, to address dysfunctional beliefs about sleep and to enhance adherence.

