**Actigraphy Sleep Assessments.** Sleep and daily physical activity will be recorded using an accelerometer (Actigraph GT9X Link, Actigraph, Pensacola, Florida), unobtrusively worn on the wrist of the non-dominant arm. The Actigraph GT9X monitor is a small, lightweight device that utilizes a 3-axis MEMS accelerometer, with motion sampled at a frequency of 30-100 Hz, and has been utilized and validated in both healthy and patient populations. Participants will wear the Actigraph 24 hours/day for 7 consecutive days, at baseline, upon completion of the 6-week run-in period, upon completion of the CBT-I intervention, and at 6-month followup. The actigraphy data will be processed using ActiLife and ActiLife+Sleep software (Actigraph, Pensacola, Florida), which was developed in collaboration with the US and international sleep and activity research community; scoring of actigraphy data will proceed in accordance with the guidelines of the Society of Behavioral Sleep Medicine. Recorded sleep log times, confirmed by an event marker, will be used to establish “lights out” and “out of bed” times. ActiLife+Sleep software will be used to derive our primary outcome measure of sleep quality, sleep efficiency (SE). Other sleep parameters of interest will be Time in Bed (TIB), total sleep time (TST), wake after sleep onset (WASO), and sleep fragmentation index (SFI). Sleep duration will be defined as TST (calculated by subtracting all periods of wakefulness from the time spent in bed). WASO is calculated by summing wakefulness periods after initial sleep onset and before final awakening. Sleep efficiency is defined as the ratio of total sleep time divided by TIB  $((TST/TIB)*100)$ . Sleep fragmentation is defined as the sum of percent mobile and percent immobile bouts less than 1-minute duration to the number of immobile bouts for a given interval. Actigraphy also provides reliable measurements of daily life physical activity and has been extensively validated against self-report, observational measures, and oxygen consumption estimates of physical activity. Therefore, the ActiLife software will also be utilized to derive daily cumulative step count and daily energy expenditure (kcal/d). All physical activity and sleep parameters derived using actigraphy will be based on the 8-consecutive-days monitoring protocol and represented as average daily activity/sleep values at each assessment phase (baseline, upon completion of the 6-week run-in period, upon completion of the CBT-I intervention, and at 6-month follow-up).

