#### C.5. ASSESSMENT OF MECHANISMS OF CARDIOVASCULAR RISK

The following laboratory-based and ambulatory assessments will be completed at baseline and repeated following the 6-week run-in control period, following the 6-week CBT-I intervention, and at 6-month follow up. Assessors will be blinded to the study phase at which data are collected.

Office BP Assessment. Automated office BP (AOBP) will be obtained using the Omron HEM-907

Professional Intellisense BP Monitor. The office BP assessment protocol is described under “Office BP Screening Assessment” described earlier in this application.

24-hour Ambulatory Blood Pressure (ABP) Monitoring. We will use the Oscar 2 ABP monitor (Suntech Medical Inc., Raleigh, NC), which has been validated previously according to US and International standards. Study participants will be instrumented with the ABP monitor between 6:00-10:00 am on a typical weekday (Mon-Fri), and the monitor will be programmed to take BP measurements every 20 minutes throughout the waking hours and every 30 minutes during the nighttime sleep period. We have used this procedure with excellent participant acceptability and compliance in numerous previous studies. A successful 24-hour study will require at least 80% of the total readings to be valid, with no more than two consecutive hours lacking a valid reading, and at least one valid measurement per hour during the nighttime sleep period. Unsuccessful ABP studies will be repeated. Because a single 24-hour ABPM record has been shown to be of greater prognostic value than multiple clinic BP readings, it has become an accepted gold standard for evaluating intervention effects on BP. In addition to mean 24-hour ABP, mean waking and mean nighttime BP will be computed, with the nighttime sleep period defined by self-reported sleep logs, in accordance with the Society for Behavioral Sleep Medicine (SBSM) guidelines. Nighttime BP dipping will be defined as the percentage of the decline in nighttime SBP ( $((\text{mean daytime SBP} - \text{mean nighttime SBP}) / \text{mean daytime SBP}) \times 100$ ); SBP dipping defined in this way is a continuous variable that will be a primary outcome measure of sleep-related CVD risk mechanisms in

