#### ANALYSIS PLAN

Data will be entered into a secure Microsoft Access database. Entry to the database is limited to key personnel and is password protected at the point of the workstation and the application. Standard double-entry and data checking approaches will be performed for all measures.

General Analytic Approach: Descriptive statistics will be performed on all study variables. In order to mitigate potential bias due to transient improvements in either sleep or BP dipping, we will utilize a 6-wk run-in phase after which participants will have their sleep efficiency and BP dipping markers re-assessed to ensure stability. Although we do not anticipate significant variation in either sleep or BP parameters during this pre-treatment phase, we will exclude participants who no longer meet inclusion criteria following the 6-wk run-in period. This practice has been shown to result in an increased magnitude of treatment improvements and therefore may improve the statistical power and potential precision of the proposed analyses. Markers of sleep efficiency and BP dipping collected after our run-in phase will therefore be used as our baseline assessment measures.

Regression-based analytic approaches will be used to examine associations between improved sleep efficiency, ABP indices, and mechanisms of CVD risk. In order to minimize potential confounding of treatment improvements due to either misdiagnosis or transient fluctuations in sleep, we will use assessments collected after the run-in period as our baseline time point. For our 6-week outcomes, improvements in sleep efficiency and ABP will be examined using simple regression analyses as detailed below. In contrast, our 6-month outcomes will be examined using repeated measures mixed models with an unstructured covariance matrix, using both 6-week and 6-month levels of the outcome modeled jointly. Incorporating both outcomes into a unified, mixed modeling approach will allow us to examine improvements in sleep as they associate with trajectories of BP dipping improvements and also allows for more robust handling of missing data.

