**Analysis Plan:** General linear models will be used to examine the associations between improvements in sleep quality on improvements in BP dipping, controlling for age, gender, race, baseline sleep efficiency, baseline mean 24-hour BP, and pretreatment BP dipping, with post-treatment BP dipping as the criterion. Significance will a priori be set at  $P = .05$ . For follow-up analyses of 6-mo BP dipping, linear repeated measures mixed models will be examined in which 6-wk and 6-mo BP dipping both serve as outcome variables using the same covariates above. As an a priori explanatory analysis for our follow-up analyses, we will examine potential time X sleep efficiency interactions in order to examine the extent to which the association between sleep efficiency and BP dipping at six weeks differs from that at six-months. In addition, we will conduct an area under the curve analysis to examine overall associations that apply to both 6-wk and 6-mo in order to determine whether larger improvements in sleep are associated with larger improvements in BP outcomes in an overall sense. Because other ABP outcomes could plausibly be improved by CBT-I and also will reflect improved nighttime dipping, we will conduct parallel analyses of nighttime average BP and 24-hour BP levels.

**AIM 2:** Evaluate candidate mechanisms of CVD risk related to sleep quality in patients with hypertension and comorbid insomnia

**Hypothesis 2:** Improved sleep quality will be accompanied by: (i) reduced nighttime SNS activity; (ii) enhanced vascular endothelial function; (iii) reduced arterial stiffness, and; (iv) improved lipid profile.

**Analysis Plan:** General linear models will be used to examine the associations between improved sleep efficiency and improvements in mechanisms of CVD risk, controlling for age, gender, race, baseline sleep efficiency, and the pre-treatment (post run-in) level of the outcome. For our analyses of vascular endothelial function only, we also will adjust for baseline arterial diameter, consistent with our prior work. Follow-up analyses will follow the same approach as in Hypothesis 1, using linear repeated measures mixed models with 6-wk and 6-mo levels serving as the outcome variables.

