Exploration of Mechanistic Relationships: For additional explanatory purposes in relation to our mechanistic conceptual model (Figure 1), we propose to conduct mediation analyses using the more commonly known Baron and Kenny approach as well as the newer MacArthur approach. By the MacArthur definition, the potential mediator must be during or post-treatment; therefore, changes in mechanisms of CVD risk occurring between baseline and 6-wk will be considered as potential mediators. The outcome then will be participants' post-treatment change in BP dipping, which will be assessed at 6-month follow-up. We will first fit a model to examine the relationship between changes in sleep efficiency and the mediator (C) (i.e., changes in mechanisms of CVD risk), as noted for Hypothesis 2. We will then fit a model examining the relationship between the mediator and post-treatment change in BP dipping. Finally, we will test for mediation using an extension of the Sobel first-order test, which examines the extent to which the associations between improved sleep efficiency and BP dipping are attributable to improvements in mechanisms of CVD risk. To fully understand these relationships, we will also investigate the MacArthur approach which is less restrictive in its assumptions, where improvements in BP dipping are attributable to improvements in mechanisms of CVD risk if there is evidence of a non-zero association between sleep efficiency and mechanisms of CVD risk, and either 1) mechanisms of CVD risk or 2) their interaction with changes in sleep efficiency also are non-zero.

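### The exploratory mediation analysis takes sleep change and mechanism change over the same interval, so it cannot show which leads to which

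*Combined protocol and SAP*

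**What the plan says.** The paragraph on mechanistic relationships in the Analysis Plan is offered as further explanation of the conceptual model. It sets the mediator's timing against treatment: "By the MacArthur definition, the potential mediator must be during or post-treatment". From this it concludes that "changes in mechanisms of CVD risk occurring between baseline and 6-wk will be considered as potential mediators". The outcome is change in BP dipping assessed at 6 months.

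The exposure is change in sleep efficiency. The paragraph gives no window for it, but says that the exposure-mediator model is the one used for Hypothesis 2. That model is fitted "controlling for age, gender, race, baseline sleep efficiency, and the pre-treatment (post run-in) level of the outcome". For the starting point, the General Analytic Approach says "we will use assessments collected after the run-in period as our baseline time point".

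The visits coincide. Actigraphy is worn "at baseline, upon completion of the 6-week run-in period, upon completion of the CBT-I intervention, and at 6-month followup" (C.4). The mechanism assessments "will be completed at baseline and repeated following the 6-week run-in control period, following the 6-week CBT-I intervention, and at 6-month follow up" (C.5).

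Two rules decide. One is an extension of the first-order Sobel test. The other is a MacArthur rule, which needs sleep change to be related to the mechanism, and either the mechanism or its interaction with sleep change to be non-zero. Both are to be read as dipping gains being due to mechanism gains. No lagged or reversed-order model is planned.

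**The concern.** The timing condition belongs to a design in which treatment is the exposure. Here treatment is constant, and D.2 names the manipulation of sleep quality as the independent variable. For the mediation reading, the mechanism change would have to follow the sleep change. Placing it after the start of CBT-I does not achieve that.

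The rival order is not far-fetched. Session 3 of CBT-I introduces relaxation, which participants continue through Sessions 4 and 5. If relaxation lowers sympathetic activity directly (my assumption, not a statement in the plan), better sleep and better dipping could both follow from the mechanism. Section A.2 itself calls the pathways interrelated. At stake is whether a positive result may be described as sleep acting on dipping through the mechanism.

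**Working it through.** **1. The interval.** Start: post run-in, from the General Analytic Approach. End for the mediator: 6 weeks, as stated. End for sleep change: the only actigraphy wave between pre-CBT-I and 6 months is the one after CBT-I. Both changes therefore run from pre-CBT-I to post-CBT-I. This is an inference for sleep, since no window is stated. The Hypothesis 2 covariates adjust for starting levels, which does not order two changes over one interval.

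Urine collection (before and after CBT-I) fits this window. Pulse wave velocity is scheduled only pre-CBT-I and at 6 months in its own C.5 paragraph, so it has no 6-week change. That is a separate point to reconcile.

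**2. The plan's own figure.** None is given for mediation. The stated power is 80% for r of at least 0.25, with 150 enrolled and 15% attrition:
- n = 150 × 0.85 = 127.5, taken as 127.
- Power = Φ(atanh(0.25) × √124 − 1.96) = Φ(0.2554 × 11.136 − 1.96) = Φ(0.884) = 0.81. The figure reproduces, and n = 127 is used below.

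**3. Why direction is not identifiable.** Let X be sleep change, M mechanism change and Y 6-month dipping, all standardised, with no direct effect of X on Y. Let r be the X-M correlation and b the M-Y link.

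| Truth | corr(X,M) | corr(M,Y) | corr(X,Y) |
|---|---|---|---|
| Sleep to mechanism to dipping | r | b | r × b |
| Mechanism to sleep, mechanism to dipping | r | b | r × b |
| Common cause of X and M (loading √r each), mechanism to dipping | √r × √r = r | b | r × b |

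With normal variables the three joint distributions are identical, so any test on X, M and Y rejects equally often under each.

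**4. Size.** Path sizes are assumptions, because the documents give none for the mechanisms. Covariates are omitted. The outcome model is taken to include both X and M, which the paragraph does not spell out. Sobel: z = a·b / √(a²·se_b² + b²·se_a²), where a is the slope of M on X and b the slope of Y on M given X. Mediation is flagged at |z| > 1.96.

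Simulated rates with both links equal:

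| Links | Sobel, either direction | Sobel plus significant total X-Y association | MacArthur rule, reversed truth |
|---|---|---|---|
| 0.25 | about 43% | about 5% | 64% |
| 0.30 | about 71% | about 14% | 85% |
| 0.35 | about 91% | about 27% | 95% |

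The third column is low because the total association is only the product of the links: 0.0625, 0.09 and 0.1225. By the formula in step 2 it is significant in about Φ(−1.26) = 10%, Φ(−0.96) = 17% and Φ(−0.59) = 28% of trials.

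A separate run of 2,500 trials per cell, with unequal and larger links, gives the three truths in the order forward / reversed / common cause:

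| Links (r, b) | Sobel | MacArthur rule |
|---|---|---|
| 0.25, 0.30 | 57 / 56 / 57% | 75 / 74 / 75% |
| 0.30, 0.30 | 72 / 72 / 72% | 86 / 85 / 86% |
| 0.40, 0.40 | 98 / 98 / 98% | 99 / 99 / 99% |

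The differences are within simulation error (√(0.57 × 0.43 / 2,500) = 1 percentage point), as step 3 requires.

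**The case against.** **The analysis is exploratory.** This stands. The paragraph is labelled explanatory, and Hypotheses 1 and 2 are worded as associations. A reader might infer that the trial's main mechanistic conclusion is compromised. The documents do not support that: mediation enters neither the primary test nor the power statement.

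**The Baron and Kenny approach may filter false results.** This stands in part. That approach is named, and the Sobel step speaks of associations between sleep and dipping, which presupposes one. Requiring a significant total association brings the rates down to about 5%, 14% and 27%. However, the paragraph lists no such step and the MacArthur rule does not need it. The requirement also removes true mediation just as often, so it does not restore direction.

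**The 43%, 71% and 91% are not error rates of the plan.** This stands. They depend on assumed links, and true mediation gives the same values. They show only that the test responds equally to either order. A reversed mechanism could be reported as mediation; it cannot be said that it would be.

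**Treatment-week diaries might supply an earlier exposure.** Session 1 teaches "the process for keeping weekly sleep diaries", so an early diary gain in sleep efficiency looks like a cure. It is only a partial one:
- Mechanism change would still be counted from pre-CBT-I and so still covers the weeks before the diary reading. With an early mechanism change driving sleep at r = 0.30, and correlated 0.5, 0.7 or 0.9 with the 6-week change (assumed), Sobel still flags mediation in about 22%, 43% and 64% of trials.
- Sleep efficiency is sleep time over time in bed, and Session 2 restricts time in bed, so diary efficiency rises partly through the restriction itself.
- C.4 describes research diaries kept alongside actigraphy. No section says that the treatment-week diaries are retained as data.

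**Conclusion.** The point holds for the exposure-mediator order in the exploratory mediation analysis, and only there. The outcome's timing is sound, since 6-month dipping follows the mediator. The conclusion rests on the inferred window for sleep change; a different window, if intended, needs to be written down. Given the shared window, the lack of direction follows from the algebra and does not depend on the assumed path sizes. Those sizes govern only how often a reversed or common-cause process would be flagged: from about 5% to about 91% for links of 0.25 to 0.35, according to whether a total association is also required. What is wrong as written is the rule that reads a positive test as dipping gains being due to mechanism gains. The planned visits cannot repair this. No mechanism is measured during CBT-I, and moving the mechanism to 6 months would make it concurrent with the outcome.

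**What to change.** In the paragraph on mechanistic relationships:
- State the window for sleep-efficiency change, and describe the analysis as an association between concurrent changes from pre-CBT-I to 6 weeks, with dipping at 6 months as the later outcome.
- Replace the wording that credits dipping gains to mechanism gains, under both the Sobel and the MacArthur rules, with wording that leaves direction open.
- Present the reversed-order model beside it (mechanism change to sleep-efficiency change to 6-month dipping, same covariates), and state that the data do not identify direction. A null reversed model must not be taken as support for the planned order. In step 3 the sleep-dipping association given the mechanism is zero under all three truths, because r × b − r × b = 0.

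Optional: a sensitivity analysis using early-treatment diary sleep efficiency, if those diaries are retained, reported with its partial ordering and the time-in-bed effect stated.

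The cost is one extra model for each mechanism examined, on data already collected, and a weaker mechanistic claim. Aims 1 and 2 and the sample size do not change.

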Power and Sample Size Considerations: Our power estimates were derived from prior data assessing sleep efficiency and nighttime BP dipping among individuals with HTN using the following assumptions: an initial sample size of 150 individuals, attrition of 15%, an alpha of 0.05, and a correlation of  $r = 0.30$  between sleep efficiency and BP dipping. Using these assumptions, we will have 80% power to detect correlations of  $r \geq 0.25$  between improvements in sleep efficiency and BP outcomes, suggesting that we will have adequate power to test the proposed hypotheses. In a more conservative scenario for comparing the worst 1/3 of the sample in terms of sleep efficiency change to the best 1/3, and assuming 50 participants in each group, there is 0.85 power at the two-sided 0.05 significance level for the detectable effect size  $\theta = 0.6$  via the following equation:  $(n \text{ per group}) = 50 = 2 * (((1.96 + 1.04) / 0.6) ** 2)$ . In the present proposal, this corresponds to a difference of 2.2% in SBP dipping between high and low sleep efficiency groups.

Exploratory Analyses of Effect Modification: In addition to our formal analyses, we will conduct exploratory analyses of effect modification, which will be interpreted as hypothesis generating. Candidate markers for effect modification will include background and clinical characteristics, such as race, gender, baseline insomnia severity, baseline anxiety, and the presence of elevated depressive symptoms ( $BDI > 14$ ). Specifically, we will examine the interaction terms between these candidate moderators, changes in sleep efficiency and mechanisms of CVD risk using the same general linear modeling approach noted for Hypothesis 2.

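### The mediation plan should name change in sleep efficiency and covariates in the mediator-outcome model, and replace the undefined Sobel extension with a bootstrap or Monte Carlo interval

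*Combined protocol and SAP*

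**What the plan says.** The mediation analysis is set out in the combined protocol and SAP, ANALYSIS PLAN, under Exploration of Mechanistic Relationships. It is offered for explanatory purposes and follows two named frameworks, Baron and Kenny and MacArthur. There are three steps.

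1. Mediator model: "We will first fit a model to examine the relationship between changes in sleep efficiency and the mediator", with the specification taken from Hypothesis 2.
2. Outcome model: "We will then fit a model examining the relationship between the mediator and post-treatment change in BP dipping". No exposure, covariate list or cross-reference is given. Dipping is taken at the 6-month follow-up.
3. Test: "we will test for mediation using an extension of the Sobel first-order test". The extension is not defined.

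Mediator change is taken from baseline to 6 weeks. The MacArthur criterion, as described there, requires a sleep-mediator association plus either a mediator effect or a mediator-by-sleep-efficiency interaction.

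The Power and Sample Size Considerations paragraph assumes "an initial sample size of 150 individuals, attrition of 15%, an alpha of 0.05, and a correlation of" 0.30. The power it claims concerns the association "between improvements in sleep efficiency and BP outcomes, suggesting that we will have adequate power to test the proposed hypotheses". It gives no path sizes, power or error rate for mediation.

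**The concern.** The trial hypothesises that improved sleep efficiency moves dipping (Hypothesis 1) and also moves the candidate mechanisms (Hypothesis 2). If both hold, sleep efficiency is a common cause of mediator and outcome. A regression of dipping on the mediator alone then credits the mediator with part of the direct sleep-dipping association. The mediator can look active when it does nothing, and it does so precisely when the trial's own hypotheses are true.

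The test is a second, separate matter. First-order Sobel treats the product of two estimated coefficients as normal. At this sample size the product is skewed and heavy-tailed, so the test rejects too rarely and can miss real mediation.

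At stake is the only analysis that asks whether the sleep-dipping association runs through a mechanism, in a study whose stated purpose is mechanistic. Two analysts reading the paragraph could fit different outcome models with very different error rates.

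**Working it through.** **Inputs.** From the documents: 150 enrolled, 15% attrition, two-sided 0.05, sleep-dipping correlation 0.30. Completers: 150 × 0.85 = 127.5, taken as 127. Assumed: the sleep-mediator path *a* and the mediator-dipping path *b*; standardised normal variables; no covariates; no unmeasured mediator-outcome confounding; the same 15% attrition at 6 months.

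**1. The plan's own figures reproduce.**
- Correlation of 0.25: Fisher z = 0.2554 × √(127 − 3) = 2.844. Power = Φ(2.844 − 1.960) = 0.81, against the stated 80%.
- Thirds of the sample: 2 × ((1.96 + 1.04)/0.6)² = 2 × 25 = 50 per group, as stated; computed power is 0.851 against 0.85.

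Neither figure concerns mediation.

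**2. Literal outcome model, no true mediation (b = 0).** With a total sleep-dipping association of 0.30, the expected coefficient in a model with the mediator alone is a × 0.30: 0.09 at a = 0.3, 0.15 at a = 0.5, 0.21 at a = 0.7. The correct value is 0.

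Hand check at a = 0.5:
- SE of b = √((1 − 0.15²)/125) = 0.0884, so z_b = 0.15/0.0884 = 1.70.
- SE of a = √((1 − 0.5²)/125) = 0.0775, so z_a = 0.5/0.0775 = 6.45.
- The Sobel statistic ab/√(b²SE_a² + a²SE_b²) equals z_a·z_b/√(z_a² + z_b²) = 10.97/6.67 = 1.64.
- Rejection ≈ Φ(1.64 − 1.96) = 0.37.

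Simulation (20,000 replicates, n = 127), Sobel at |z| > 1.96; the row with both values at 0.25 uses a sleep-dipping correlation of 0.25, the others 0.30:

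| a | sleep-dipping r | dipping on mediator only | dipping on mediator + sleep change |
|---|---|---|---|
| 0.25 | 0.25 | 4.1% | 1.0% |
| 0.30 | 0.30 | 10.1% | 2.0% |
| 0.40 | 0.30 | 21.5% | 2.9% |
| 0.50 | 0.30 | 36.2% | 4.2% |
| 0.70 | 0.30 | 65.6% | 5.0% |

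A separate run of 4,000 replicates gave 2.5% (a = 0.2) and 5.4% (a = 0.25) for the mediator-only model at a correlation of 0.30. Inflation therefore starts at a path somewhere between 0.25 and 0.30.

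**3. Sobel against alternatives, exposure included, true mediation, no direct effect.** Hand check at a = b = 0.25:
- SE_a = √(0.9375/125) = 0.0866, z_a = 2.89.
- SE_b = √(0.9375/(124 × 0.9375)) = 0.0898, z_b = 2.78.
- Sobel z = (2.89 × 2.78)/√(2.89² + 2.78²) = 8.03/4.01 = 2.00, barely past 1.96.
- Requiring each path to be significant: Φ(0.93) × Φ(0.82) = 0.82 × 0.79 = 0.65.

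| a = b | Sobel | Monte Carlo product interval | joint significance |
|---|---|---|---|
| 0.25 | 0.42-0.43 | 0.60-0.63 | 0.64 |
| 0.30 | 0.72 | 0.84 | 0.85 |

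With a direct effect that brings the total to 0.30, the gap is similar: Sobel 0.45 against joint significance 0.67 at paths of 0.25, and 0.75 against 0.87 at 0.30. The product interval's type I error, with a non-zero sleep-mediator path and b = 0, was about 0.04 to 0.06.

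**4. What adding the exposure does to Sobel power.** With no direct effect: 45.7% to 42.6% at a = b = 0.25, 75.5% to 71.6% at 0.30, 98.8% to 97.8% at 0.40. Falls are larger where there is a direct effect and a strong sleep-mediator path, such as 91.9% to 50.2% at a = 0.50, b = 0.20, total 0.30. There the mediator-only model estimates 0.30 for a path whose true value is 0.20, so much of the higher rejection rate is confounding.

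**5. Timing.** CBT-I lasts 6 weeks, and mediator change is measured over the same 6 weeks as change in sleep efficiency. The data can place dipping at 6 months after both, but cannot order the two changes themselves.

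**The case against.** The strongest reply is that the error is read from silence. The sentence speaks of a relationship, not a formula. Baron and Kenny's mediator-outcome step conditions on the exposure. The MacArthur criterion uses an interaction with sleep efficiency, which cannot be fitted without it. The paragraph also says the test concerns how far the sleep-dipping association is attributable to the mechanism, which needs both variables. This stands: the plan is under-specified and at odds with its own labels. A reader might infer that it commits to a wrong model; the documents do not support that.

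Three further inferences are tempting and should be resisted.
- That Sobel produces false mediation. It does not. With the exposure included it rejects in 1-5% of null trials; the omitted exposure is the cause.
- That putting the exposure in costs much of the power. At modest paths with no direct effect the cost is 1-4 points, and the documents claim no mediation power that could be lost.
- That the primary result is at risk. The analysis is labelled explanatory, Aim 2 tests the mechanisms directly, and the powered claims do not use it.

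It is also fair that the larger false-positive rates need a path of 0.5, twice the correlation of 0.25 for which the plan claims 80% power, and that the Sobel extension is undefined, so the calculations use the plain first-order form.

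What remains is that a prespecified plan should settle which model is fitted, and that a better test is available at almost no cost.

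**Conclusion.** The point holds as a specification gap plus an inefficient test. Read literally, the outcome step would give false mediation in about 10% of trials (sleep-mediator path 0.3) to 36% (path 0.5) instead of 2-5%, with little or no inflation at 0.25 or below. Independently of that, replacing first-order Sobel raises power by about 0.21 (0.42 to 0.63) with both paths 0.25 and about 0.12 (0.72 to 0.84) with both 0.30. These sizes rest on the assumed paths and the simplifying assumptions listed with the inputs; covariates, other attrition at 6 months or a different Sobel extension would shift them. The change is worth making before analysis because the study's purpose is mechanistic, but nothing in Aim 1 or its stated power depends on it.

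**What to change.** In Exploration of Mechanistic Relationships:

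- State the outcome model as 6-month BP dipping on mediator change + change in sleep efficiency + the Hypothesis 1 covariates (age, gender, race, baseline sleep efficiency, baseline mean 24-hour BP, pretreatment dipping).
- Replace the Sobel extension with a percentile-bootstrap or Monte Carlo 95% interval for the indirect effect.
- Fit the mediator-by-sleep-efficiency interaction for the MacArthur criterion as a separate model, with change in sleep efficiency mean-centred. In one check that assumed a mean sleep-efficiency change of 1 SD, an uncentred interaction cut product-interval power at a = b = 0.25 from 0.62 to 0.39; centred, it was 0.61.
- Say that results will be reported as consistent with mediation only, because exposure and mediator changes span the same 6 weeks, and that the study was not powered for indirect effects.

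The cost is a few sentences of SAP text and a few lines of R or SAS. The trade-off is an interval whose type I error sits near 5% (up to about 6% in simulation) where Sobel's usually sits below it.
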